6.0 Study Drug Duration and Compliance

6.1 Study Drug Duration

12-Week Induction Period:

For the safety population SA1A, the duration of exposure to study drug will be summarized for each treatment group in the 12-Week Induction Period. The study drug dose date refers to recorded dates of infusion/injections of study drug.

- Duration of exposure in the 12-Week Induction Period:
 - If the subject enrolled into M16-000 after the 12-Week Induction Period:
 - Duration of exposure = min(the first study drug dose date in M16-000 – the first study drug dose date in the 12-Week Induction Period, the last study drug dose date in the 12-Week Induction Period –

- the first study drug dose date in the 12-Week Induction Period +28 days),
- If the subject enrolled into the Induction Period 2 after the 12-Week Induction Period:
 - Duration of exposure = min(the first study drug dose date in the Induction Period 2 – the first study drug dose date in the 12-Week Induction Period, the last study drug dose date in the 12-Week Induction Period – the first study drug dose date in the 12-Week Induction Period +28 days),
 - Otherwise:
 - Duration of exposure = the last study drug dose date in the 12-Week Induction Period – the first study drug dose date in the 12-Week Induction Period +28 days.

For each treatment group and total in this induction period, the duration of exposure will be summarized by the number of subjects treated, as well as the mean, standard deviation, median, minimum and maximum values. In addition, the number and percentage of subjects exposed to study drug will be summarized for the following exclusive duration intervals:

- 1 – 28 days
- 29 – 56 days
- 57 – 84 days
- 85 – 112 days
- >112 days

Induction Period 2:

For the safety population SA2A, the duration of exposure to study drug will be summarized for each treatment group in the Induction Period 2. The study drug dose date refers to recorded dates of infusion/injections of study drug.

- Duration of exposure in the Induction Period 2:
 - If the subject enrolled into M16-000 after the Induction Period 2:
 - Duration of exposure = min(the first study drug dose date in M16-000 – the first study drug dose date in the Induction Period 2, the last study drug dose date in the Induction Period 2 – the first study drug dose date in the Induction Period 2 +28 days [for IV dose] or 56 days [for SC dose]),
 - Otherwise:
 - Duration of exposure = the last study drug dose date in the Induction Period 2 – the first study drug dose date in the Induction Period 2 +28 days (for IV dose) or 56 days (for SC dose).

For each treatment group and total in the Induction Period 2, the duration of exposure will be summarized by the number of subjects treated, as well as the mean, standard deviation, median, minimum and maximum values. In addition, the number and percentage of subjects exposed to study drug will be summarized for the following exclusive duration intervals:

- 1 – 28 days
- 29 – 56 days
- 57 – 84 days
- 85 – 112 days
- >112 days

ALL Risankizumab:

For all risankizumab population SA-ALL, the duration of exposure to study drug will be summarized for all risankizumab treatment group over the whole course of the study. The study drug dose date refers to recorded dates of infusion/injections of study drug.

- Duration of exposure for all risankizumab:
 - If the subject enrolled into M16-000:

- Duration of exposure = min(the first study drug dose date in M16-000 – the first risankizumab dose date in M16-006, the last risankizumab dose date in M16-006 – the first risankizumab dose date in M16-006 +28 days [if the last dose is IV dose] or 56 days [if the last dose is SC dose]),
- Otherwise:
 - Duration of exposure = the last risankizumab dose date in M16-006 – the first risankizumab dose date in M16-006 +28 days [if the last dose is IV dose] or 56 days [if the last dose is SC dose].

The duration of exposure will be summarized by the number of subjects treated, as well as the mean, standard deviation, median, minimum and maximum values. In addition, the number and percentage of subjects exposed to risankizumab will be summarized for the following exclusive duration intervals:

- 1 – 28 days
- 29 – 56 days
- 57 – 84 days
- 85 – 112 days
- 113 – 140 days
- 141 – 196 days
- >196 days

6.2 Study Drug Compliance

The treatment compliance (%) of study drug information will be summarized for safety populations SA1 and SA2:

6.2.1 Intravenous Therapy

- Percent of subjects who received full volume
- Average infusion duration (hours)
- Treatment compliance (%)

6.2.2 Subcutaneous Therapy

- Total number of injections received
- Treatment compliance (%)

7.0 Demographics, Baseline Characteristics, Medical History, and Prior/Concomitant Medications

Demographics and baseline or disease characteristics will be summarized for the ITT1A, ITT1B, ITT2A, ITT2B, SA1A population overall and by treatment group. Medical history and prior medications will be summarized for the ITT1A population overall and by treatment group. Concomitant medications will be summarized for the ITT1A and ITT2 population overall and by treatment group. Categorical variables will be summarized with the number and percentage of subjects; percentages will be calculated based on the number of non-missing observations. Continuous variables will be summarized with descriptive statistics (number of non-missing observations, mean and standard deviation, median, minimum and maximum).

7.1 Demographics and Baseline Characteristics

The following demographic and baseline or disease characteristics will be summarized at the baseline of the study, where the baseline refers to the last non-missing observation before the first administration of any study drug.

Demographics

- Age (years)
- Age category [< 18 , [18, 40), [40, 65), ≥ 65]
- Sex [male/female]
- Race [American Indian/Alaska Native, Asian, Black or African American, Native Hawaiian or Other Pacific Islander, White, Multiple]
- Ethnicity [Hispanic/Latino, Non-Hispanic/Latino]
- Geographic region (as defined in [Appendix I](#))

Tobacco/Nicotine and Alcohol Use

- Tobacco/Nicotine Use [currently smokes, ex-smoker, never smoked, unknown]
- Alcohol Use [current drinker, former drinker, non-drinker, unknown]

Vital Signs

- Systolic and diastolic blood pressure (mmHg)
- Pulse (bpm)
- Body temperature (°C)
- Body weight (kg) – overall and by sex
- Body weight category (< 60 kg, ≥ 60 kg)
- Height (cm)
- Body Mass Index (kg/m²)
- BMI Category
 - Underweight [< 18.5 kg/m²]
 - Normal [≥ 18.5 and < 25 kg/m²]
 - Overweight [≥ 25 and < 30 kg/m²]
 - Obese [≥ 30 kg/m²]

Patient Reported Outcomes at Baseline

- IBDQ – total score and domain scores
- WPAI-CD – 4 sub-scores
- CSS – total score
- FACIT-Fatigue – total score and 13 item scores
- EQ-5D-5L – Index score and Vas Pain
- SF-36 – 8 domain scores, PCS and MCS
- Average Daily Stool Frequency
- Average Daily Abdominal Pain

Other Assessments at Baseline

- CDAI
- SES-CD
- Crohn's Disease Duration (years)
- Fecal calprotectin
- Baseline corticosteroid use (yes, no)
- Baseline immunomodulator use (yes, no)
- Biologics failure history (0, 1, >1)
- TNF failure history (0, 1, >1) within bio-IR population
- Vedolizumab failure history (yes, no) within bio-IR population
- Ustekinumab failure history (yes, no) within bio-IR population
- hs-CRP
- Draining fistulas (yes, no)
- Non-draining fistulas (yes, no)
- Anal fissures (yes, no)
- Crohn's Disease Location Per SES-CD (colonic only, ileal only, ileal-colonic)
- Extra Intestinal Manifestation (yes, no)

In addition, some clinical tests at baseline such as TB test, pregnancy test and electrocardiogram assessment will be summarized. Crohn's Disease history (Montreal classification) and Crohn's Disease surgical history will be summarized separately as well.

7.2 Medical History

Medical history data will be coded using the Medical Dictionary for Regulatory Activities (MedDRA). The actual version of the MedDRA coding dictionary will be noted in the statistical tables and clinical study report. The number and percentage of subjects in each medical history category (by MedDRA system organ class and preferred term) will be summarized overall and by treatment group. The system organ class (SOC) will be presented in alphabetical order, and the preferred terms will be presented in alphabetical

order within each SOC. Subjects reporting more than one condition/diagnosis will be counted only once in each row (SOC or preferred term).

7.3 Prior and Concomitant Medications

Prior and concomitant medications will be summarized by generic name. A prior medication is defined as any medication taken prior to the date of the first dose of any study drug. A concomitant medication for 12-Week Induction Period is defined as any medication other than study drug that (1) was started prior to the first dose of study drug and continued to be taken after the first dose of study drug in the 12-Week Induction Period or (2) was started after the first dose of study drug during the 12-Week Induction Period, but prior to the first dose of Induction Period 2 if the subject enters Induction Period 2 or prior to the first dose of M16-000 if the subject enters M16-000, or prior to the last dose + 140 days if the subject does not enter Induction Period 2 nor M16-000.

A concomitant medication for Induction Period 2 is defined as any medication other than study drug that (1) was started prior to the first dose of study drug in Induction Period 2 and continued to be taken after the first dose of study drug in Induction Period 2 or (2) was started after the first dose of study drug in Induction Period 2, but prior to first dose of M16-000 if the subject enters M16-000, or last dose + 140 days if the subject does not enter M16-000. Information about concomitant medications can be collected up to 140 days after last dose, as per protocol.

The number and percentage of subjects taking medications will be summarized by generic drug name based on the World Health Organization (WHO) Drug Dictionary for both prior and concomitant medications.

8.0 Efficacy Analyses

8.1 General Considerations

The primary and secondary efficacy endpoints as specified in Section 3.1 and Section 3.2 will be analyzed based on ITT1A for 12-Week Induction Period. The difference between

treatment groups for the primary and ranked secondary efficacy endpoints will be tested with graphical multiplicity adjustment¹ to ensure a strong control of family-wise type I error rate at significance level $\alpha = 0.05$ (two-sided) (see Section 11.0). Analyses of other efficacy endpoints for 12-Week Induction Period as specified in Section 3.3 will be performed using ITT1A at the nominal significance level $\alpha = 0.05$ (two-sided) without multiplicity adjustment.

Analyses for other efficacy endpoints as specified in Section 3.3 for Induction Period 2 will be performed using ITT2A. Since the Induction Period 2 is for exploratory purpose, no multiplicity adjustment will be performed.

For all efficacy endpoints, the descriptive statistics will be provided by period and by treatment group in which the subjects were randomized to at the beginning of each period. The statistics include number of observations, mean, standard deviation, minimum, median, and maximum for continuous variables, and number and percent for discrete variables.

Unless otherwise specified, any subject who is randomized based on a wrong stratum will be analyzed according to the actual stratum the subject belongs to.

When all subjects complete their Week 12/PD visit, the database will be locked and un-blinded for the 12-Week Induction Period. The planned analysis for the 12-Week Induction Period will be performed. This is the only and final efficacy analysis for the 12-Week Induction Period. When all the subjects who enter the Induction Period 2 finish Week 24/PD visit, the database will be locked for the whole study and all the planned analysis for the Induction Period 2 will be performed.

Analysis of Binary Variables:

For binary variables, frequencies and percentages will be reported for each treatment group. Pairwise comparison of each risankizumab group and placebo will be performed using the Cochran Mantel-Haenszel (CMH) test adjusting for stratification factors. If there is a stratum for a treatment group that has no subject in it, a value of 0.1 will be

added to all cells in the corresponding table in order to prevent dividing by 0, as suggested in Greenland and Robins (1985)³. Point estimates and 95% confidence interval (CI)s for the difference in proportions between each of risankizumab treatment groups and placebo will be provided. Construction of CI for the common risk difference will be based on the Mantel-Haenszel estimate adjusting for stratification factors. For binary endpoints with small number of sample size (such as achievement of no draining fistulas at Week 12 in subjects with draining fistulas at baseline), or small number of responders (such as occurrence of CD-related hospitalization through Week 12), Chi-square test (or Fisher's exact test if $\geq 20\%$ of the cells have expected cell count < 5) will be performed.

Analysis of Continuous Variables:

For continuous variables, the model based mean and standard error will be provided. The baseline and visit means will also be presented for each treatment group. Continuous variables collected longitudinally will be using a Mixed-Effect Model Repeated Measurement (MMRM) model. Continuous efficacy variables which are collected at only one post-baseline visit (such as SES-CD) will be analyzed using an Analysis of Covariance (ANCOVA) model. Point estimates and 95% CIs of mean change from baseline within treatment groups, and between each risankizumab treatment group and placebo will be provided. The baseline refers to the last non-missing observation before the first administration of any study drug or randomization if no study drug is given.

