2.2 Study Design Overview

This is a Phase 3, multicenter, randomized, double-blind, placebo-controlled study designed to evaluate the efficacy and safety of risankizumab as an induction therapy in subjects with moderately to severely active CD.

The study consists of the following periods:

1. Screening period of up to a maximum of 35 days
2. 12-week randomized, double-blinded IV therapy induction period (12-Week Induction Period)
3. 12-week randomized, double-blinded, double-dummy Induction Period 2 (Induction Period 2) for subjects who do not achieve clinical response at Week 12
4. 20-week follow up period from the last dose of study drug.

The schematic of the study is shown in [Figure 1](#).

Figure 1. Study Schematic

[figure not shown]
[figure not shown]

Figure 1. Study Schematic (Continued)

DC = discontinued; IR = subjects with inadequate clinical response to induction; IV = intravenous; R = subjects with clinical response; RR = re-randomize

Approximately 855 patients with moderate to severe CD who had baseline eligible SES-CD (eligible SES-CD is defined as total SES-CD score excluding presence of narrowing subscore) of ≥ 6 (≥ 4 for isolated ileal disease) are to be randomized in a ratio of 2:2:1 to one of the three following treatment groups in the 12-Week Induction Period.

- Placebo IV (n = 342)
- Risankizumab 600 mg IV (n = 342)
- Risankizumab 1200 mg IV (n = 171)

In addition to the 855 subjects, up to 85 subjects with a lower SES-CD, defined as an eligible SES-CD of ≥ 3 to < 6 for ileocolonic or colonic disease or SES-CD of 3 for isolated ileal disease will be enrolled in order to inform treatment effect in this patient population, but these subjects will not be included in the primary ITT population for efficacy analysis.

Each treatment group receives the corresponding dose of risankizumab or placebo IV infusion at Week 0, Week 4, and Week 8. At Week 12, patients are evaluated for clinical response, defined as $\geq 30\%$ decrease in average daily SF and/or $\geq 30\%$ decrease in average daily AP score and both not worse than baseline.

Visits for clinical evaluation will occur at baseline/Week 0, Weeks 4, 8, and 12 or Premature Discontinuation (PD).

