Subjects, who do not achieve clinical response at Week 12 will be randomized by Interactive Response Technologies (IRT) to the Induction Period 2, a double-blind, double dummy 12-week treatment period. Subjects who received risankizumab induction treatment during the 12-Week Induction Period will be randomized 1:1:1 to:

- Risankizumab 1200 mg IV
- Risankizumab 360 mg subcutaneous (SC)
- Risankizumab 180 mg subcutaneous (SC)

Subjects who received placebo induction treatment during the 12-Week Induction Period will receive:

- Risankizumab 1200 mg IV

The IV risankizumab dose or matching IV placebo will be given at Weeks 12, 16, and 20; The SC risankizumab dose or matching SC placebo will be given at Weeks 12, and 20.

At Week 24, subjects who participated in the blinded Induction Period 2 will be reassessed and undergo a third endoscopy for evaluation of mucosal inflammation. Subjects who achieve clinical response at Week 24 may be eligible to enter the Study M16-000. Subjects without clinical response at Week 24, as well as all subjects who are terminated the study early (including subjects who are eligible for but do not participate in the blinded Induction Period 2), will be discontinued and have a follow-up call 140 days

from the last dose of study drug to obtain information on any new and/or ongoing adverse events (AEs).

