5.0 Subject Disposition

The total number of subjects who were enrolled, randomized and treated will be summarized.

A summary of subject accountability will be provided where the number of subjects in each of the following categories will be summarized for each treatment group:

- Subjects enrolled/randomized in the study
- Subjects who took at least one dose of study drug (ITT1A for the 12-Week Induction Period, ITT2 for the Induction Period 2 and ITT1 for the entire study)
- Subjects who completed study drug (SA1A for the 12-Week Induction Period, SA2 for the Induction Period 2 and SA1 for the entire study)
- Subjects who prematurely discontinued study drug (SA1A for the 12-Week Induction Period, SA2 for the Induction Period 2 and SA1 for the entire study)
- Subjects who prematurely discontinued from study (ITT1A for the 12-Week Induction Period, ITT2 for the Induction Period 2 and ITT1 for the entire study)
- Subjects who completed study (ITT1A for the 12-Week Induction Period, ITT2 for the Induction Period 2 and ITT1 for the entire study)

For end of study participation, the number and percentage of subjects who completed the protocol defined follow-up period (or did not with associated reasons) will be summarized overall and by treatment group.

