9.2.1 Treatment-Emergent Adverse Events

12-Week Induction Period: Treatment emergent AEs (TEAEs) for the 12-Week Induction Period are defined as events that begin either on or after the first dose of the study drug in the 12-Week Induction Period and until the first dose of study drug in the Study M16-000 if the subject is enrolled into the Study M16-000 or until first dose of study drug in Induction Period 2 if the subject is enrolled into Induction Period 2, or within 140 days after the last dose administration of the study drug in 12-Week Induction Period if the subject does not participate in the Study M16-000 or the Induction Period 2.

Induction Period 2: Treatment-emergent AEs (TEAEs) for the Induction Period 2 are defined as events that begin either on or after the first dose of the study medication in the Induction Period 2 and until first dose of study drug in the Study M16-000 if the subject is enrolled into the Study M16-000 or within 140 days after the last dose of the study drug in the Induction Period 2 if the subject does not participate in the Study M16-000.

All Risankizumab: Treatment-emergent AEs (TEAEs) for "All Risankizumab" are defined as events that begin either on or after the first dose of risankizumab and until first dose of study drug in the Study M16-000 if the subject is enrolled into the Study M16-000 or within 140 days after the last dose of risankizumab in the study if the subject does not participate in the Study M16-000.

Events where the onset date is the same as the study drug start date are assumed to be treatment-emergent, unless the study drug start time and the adverse event start time are collected and the adverse event start time is prior to the study drug start time. If an incomplete onset date was collected for an adverse event, the event will be assumed to be treatment-emergent unless there is other evidence that confirms that the event was not treatment-emergent (e.g., the event end date was prior to the study drug start date).

All treatment-emergent AEs will be summarized overall, as well as by primary MedDRA SOC and Preferred Term. The SOCs will be presented in alphabetical order, and the PTs will be presented in alphabetical order within each SOC.

The number and percentage of subjects experiencing treatment-emergent AEs will be summarized. The risk difference and 95% CI between each risankizumab group and placebo group will be presented.

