9.2.2 Adverse Event Overview

An overview of AEs will be presented consisting of the number and percentage of subjects experiencing at least one event for each of the following AE categories:

- Any treatment-emergent AE
- Any treatment-emergent AE related to COVID-19
- Any treatment-emergent AE related to study drug according to the investigator
- Any severe treatment-emergent AE
- Any serious treatment-emergent AE
- Any treatment-emergent AE leading to discontinuation of study drug
- Any treatment-emergent AE leading to death
- Treatment-emergent AEs of Safety Interest including
 - Adjudicated MACE events
 - Serious infections
 - Active Tuberculosis
 - Opportunistic infections excluding tuberculosis and herpes zoster
 - Malignant tumors
 - Malignancies excluding NMSC
 - Hypersensitivity – serious events only
 - Adjudicated anaphylactic reaction
 - Serious anaphylactic reaction
- All deaths
 - Deaths occurring \leq 140 days after last dose of study drug
 - Deaths occurring $>$ 140 days after last dose of study drug
 - Deaths related to COVID-19

The exposure adjusted rate for AE overview will be presented as well.

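### The whole-study database lock at the last Week 24/PD visit conflicts with the SAP's own 140-day safety follow-up, leaving the reporting window incomplete for late subjects who do not enter M16-000

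*SAP*

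**What the plan says.** Section 8.1 sets two locks. The first comes when all subjects have had their Week 12/PD visit and serves the 12-Week Induction Period. The second is the final one: "When all the subjects who enter the Induction Period 2 finish Week 24/PD visit, the database will be locked for the whole study". The same sentence has all planned Induction Period 2 analyses performed at that point.

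Other sections describe a study that runs longer:

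- Section 2.2 lists as its fourth period a "20-week follow up period from the last dose of study drug". Week 24 non-responders and early terminations "will be discontinued and have a follow-up call 140 days" after the last dose, to collect new and ongoing adverse events.
- Section 9.2.1 counts Induction Period 2 events as treatment-emergent if they begin "within 140 days after the last dose of the study drug in the Induction Period 2 if the subject does not participate" in M16-000. The all-risankizumab definition has the same limit.
- Section 9.2.2 splits deaths at "140 days after last dose of study drug", reporting those before and those after.
- Section 7.3 takes concomitant medication to last dose + 140 days.
- Section 5.0 reports "the number and percentage of subjects who completed the protocol defined follow-up period", with reasons for those who did not.
- Section 9.2.4 counts exposure to last dose + 140 days or the first dose of the next period or study, whichever is earlier. It has no cut at the lock date.
- Section 9.1 places the 12-Week Induction Period safety analyses at database lock and says missing safety data are not imputed. It gives no date for the Induction Period 2 safety analysis.

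**The concern.** A lock for the whole study that precedes the end of one of its periods cannot deliver tables defined over that period. Safety is part of the stated objective. Taken at its word, the rule has the final safety tables for SA2, SA2A and SA-ALL built while some subjects are still inside the window that defines their treatment-emergent events.

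The subjects exposed to this are those who do not roll over to M16-000: Week 24 non-responders and discontinuers. For those who do roll over, the window closes at the first M16-000 dose.

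The exposure rule adds a second effect. If events stop at the lock but exposure runs to last dose + 140 days, unobserved time enters the denominator without its events, and exposure-adjusted rates come out too low.

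**Working it through.** **Inputs.** Dosing (Section 2.2): "The IV risankizumab dose or matching IV placebo will be given at Weeks 12, 16, and 20" and "The SC risankizumab dose or matching SC placebo will be given at Weeks 12, and 20". Follow-up: 20 weeks or 140 days after the last dose. Lock: last Week 24/PD visit (Section 8.1).

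**Consistency of the follow-up length.** 140 / 7 = 20 weeks, so the SAP's two statements agree.

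**Gap for a subject dosed at Week 20 and seen at Week 24.**
- Window ends: 20 + 20 = Week 40.
- Gap after the Week 24 visit: 40 − 24 = 16 weeks = 112 days.
- Share of the post-dose window: 112 / 140 = 80%.
- Share of the whole Induction Period 2 event window: length 56 + 140 = 196 days, observed by Week 24 = 84 days, unobserved = 112 / 196 = 57%. Section 9.2.4 would still count all 196 days as exposure.

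These are the figures for the last such subject before the lock. They shrink to zero for a subject whose Week 24 visit was 16 weeks or more before it.

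**Gap for a PD visit.** If the visit comes 4 weeks after a dose, 20 − 4 = 16 weeks. If it comes right after a dose, the gap approaches 20 weeks.

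**Subjects dosed only in the first period.** Last dose at Week 8 gives a window to Week 28. If such a subject was enrolled alongside the last Induction Period 2 subject, about 28 − 24 = 4 weeks remain open at the whole-study lock.

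**The Week 12 lock.** 8 + 20 = Week 28, and 28 − 12 = 16 weeks. The same gap applies to the 12-Week Induction Period safety analysis, for subjects who enter neither Induction Period 2 nor M16-000.

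**How many are affected.** The SAP gives no accrual duration. Assume Week 24 visits are uniform over T weeks and all doses were given. The share of non-continuing Induction Period 2 subjects with an open window is 16 / T. Their mean loss is 16 / 2 = 8 weeks. Averaged over all non-continuing subjects, the unobserved part of the 28-week (196-day) window is (16 / T) × 8 / 28.

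| T (weeks, assumed) | Share with open window | Average part of window unobserved |
|---|---|---|
| 52 | 31% | 8.8% |
| 104 | 15% | 4.4% |
| 156 | 10% | 2.9% |

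**The case against.** The strongest reply is that Section 8.1 sits in the efficacy chapter, that the rest of the SAP plainly expects the follow-up data, and that the protocol may set a later safety lock. On that view this is one loosely worded sentence. That may well be the explanation, but it does not remove the conflict: the sentence covers the whole study and all planned Induction Period 2 analyses, and the SAP names no later lock, safety update or censoring date. If a later lock exists, the sentence needs correcting.

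Four stronger readings are tempting and not supported:

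- *Late events and deaths will certainly be missing from the final results.* This follows only if the sentence is applied literally. Section 9.1 does not date the Induction Period 2 safety analysis, and the protocol is not at hand.
- *All Week 24 non-responders and early discontinuers lose follow-up.* Those who finished their 140 days before the lock do not.
- *The comparison between randomised arms is biased.* All Induction Period 2 arms have their last scheduled dose at Week 20, and truncation follows calendar time. No figure in the SAP shows a difference by arm, and this period has no concurrent placebo group.
- *The disposition table would count ongoing subjects as not having completed follow-up.* Section 5.0 does not say how they are classified.

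The number of lost events also cannot be estimated, because the SAP gives neither event rates nor the number of non-continuing subjects.

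**Conclusion.** The conflict inside the SAP is real and should be corrected. Its literal effect is an incomplete adverse-event, death and follow-up window for subjects who do not enter M16-000 and whose last dose was within 140 days of the lock: up to 16 weeks, or close to 20 after an early PD visit. The exposure rule in Section 9.2.4 makes this worse by counting the unobserved time.

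The 16-week figure rests only on the SAP's schedule. The 31%, 15% and 10% shares rest on an assumed uniform accrual. Subjects who enter M16-000, earlier enrollees who have finished follow-up, and the Week 12 primary efficacy analysis are unaffected.

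**What to change.** In Section 8.1:

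- Keep the Week 12 lock for the primary analysis and, if wanted, a Week 24 lock limited to Induction Period 2 efficacy.
- Define the whole-study lock as the point when every subject has either received a first M16-000 dose or completed (or been lost to) the 140-day follow-up.
- Produce the final safety and disposition tables for all periods, including the 12-Week Induction Period, from that lock.

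In Sections 9.1 and 9.2.4, state that any safety table made from an earlier lock cuts both events and exposure at the data cut-off date.

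The cost is SAP wording and a delay of about 16 to 20 weeks in the final safety tables. The follow-up call is already planned, so no visit is added, and the date of the primary analysis does not move.
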